 - To characterise the efficacy and safety profile of extended pharmacological thromboprophylaxis in patients at high risk for VTE.

3. Project Timeline:

- The suggested overall data collection periods will be Monday 24th January 2022 to 3rd April 2022. Each mini-team will collect data over a 14-day, consecutive period with subsequent 30-day follow-up:
 - Period 1: 00:00 24th Jan 2022 - 23:59 06th Feb 2022 (+ 30 Day Follow-up)
 - Period 2: 00:00 07th Feb 2022 - 23:59 20th Feb 2022 (+ 30 Day Follow-up)
 - Period 3: 00:00 21st Feb 2022 - 23:59 06th Mar 2022 (+ 30 Day Follow-up).
 - Period 4: 00:00 07th Mar 2022 - 23:59 20th Mar 2022 (+ 30 Day Follow-up).
 - Period 5: 00:00 21st Mar 2022 - 23:59 03rd Apr 2022 (+ 30 Day Follow-up).
- Patients should be included if their operation started (defined as 'knife-to-skin' time) within

the time period during the data collection periods as specified above.

- Additional data collection periods may be added later in the study, to give flexibility to include further centres, who have had logistical difficulties in study start up.
 - Period 6: 00:00 18th Apr 2022 - 23:59 01st May 2022 (+ 30 Day Follow-up).
 - Period 7: 00:00 2nd May 2020 – 23:59 15th May 2022 (+ 30 Day Follow-up).

4. Centre Eligibility:

- CASCADe is open to any hospital in UK and Europe that routinely performs either elective and emergency major abdominal surgery.
- All participating centres are required to register the CASCADe audit according to local regulations. In the UK, CASCADe has been confirmed by the NHS East of Scotland REC Committee that it does not need NHS ethical review under the terms of the Governance Arrangements for Research Ethics Committees (**Appendix F**).
- Internationally, individual study investigators are responsible for ensuring the correct audit, ethical or departmental approval has been achieved prior to commencing data collection (this can be registered as an audit, quality improvement project or service evaluation, if appropriate).
- Evidence of successful audit registration must be sent to study management team (or the appropriate regional lead for UK centres) prior to commencement of data collection. Centres will not be allowed to upload patients’ data onto REDCap without evidence of successful registration of the study.
- Following completion of the CASCADe audit, it is a requirement of participation that mini-teams should **present the audit findings** to the surgery and/or audit departments at each centre.

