 - Staged with a planned return for reoperation (such as but not limited to damage control laparotomy or burns surgery) OR
 - Change in operative plan such that during the first procedure it is determined that a reoperation is necessary, even if the patient was enrolled preoperatively
- **Return to theatre:** Each individual patient should only be included in the study *once*. Patients returning to theatre due to complications following earlier surgery can be included, as long as their indexed procedure has not already been included in the CASCADE audit.

You should collect data on consecutive patients operated at your centre during the data collection period. This means that all eligible patients should be included.

Strategies to identify consecutive eligible patients could include:

- *Daily review of elective theatre lists.*
- *Daily review of handover sheets/ emergency admission and ward lists.*
- *Daily review of theatre logbooks (both elective and emergency).*

6. Covariates:

Data will be collected on audit standards and confounding factors for risk-adjusted analyses. These include age, sex, ethnicity, body mass index, American Society of Anaesthesiologists (ASA) grade, relevant comorbidities, smoking status, anticoagulant or antiplatelet use, preoperative blood test values, and preoperative anaemia management. Variables including operative urgency, operative procedure, operative contamination, use of tranexamic acid, intraoperative blood transfusions used, haemoglobin level at transfusion, duration of procedure and post-operative iron therapy will also be collected. Without appropriately adjusting for risk factors, it is likely that any findings would be biased and unable to be appropriately analysed on a national scale. A full list of required data fields is available in **Appendix B**, and on the REDCap database.

7. Outcome Measures and Follow-up:

Primary outcome measure:

- Rates of compliance to pre-, intra-, and postoperative audit standards in reducing risk of postoperative cardiovascular complication.

Secondary outcome measures:

- Incidence of postoperative cardiovascular complications within 30-days of surgery according to the Standardized Endpoints for Perioperative Medicine (StEP) cardiovascular.¹³ (see **Appendix D: Definitions of Key Outcomes**).
- 30-day postoperative blood transfusion rates
- 30-day complication rates defined according to the Clavien-Dindo classification (see **Appendix D: Definitions of Key Outcomes**)

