Appendix B: Data Dictionary

Pre-operative Data Fields	Required data (definition / comment)	Suggested source(s)
1. Patient age	Years (whole years at the time of operation)	– Clinical letters / notes
2. Patient sex	Male / Female	– Clinical letters / notes
3. Patient body mass index (BMI)	kg/m² (record to two decimal places)	– Drug charts – Clinical letters / notes
4. Patient ASA grade	Grade I-V (Full ASA classification available at: https://www.asahq.org/resources/clinical-information/asa-physical-status-classification-system)	– Anaesthetic notes
5. Smoking status	Current (≤6 weeks, >6 weeks), Previous, Never	– Admissions clerking – Clinical notes
6. Clinical Frailty scale	1-3 / 4-6 / 7-9 (Full Clinical frailty scale available at: https://www.dal.ca/sites/gmr/our-tools/clinical-frailty-scale.html)	– Admissions clerking – Clinical notes
7. History of cardiovascular disease	Yes (myocardial infarction, angina, congestive cardiac failure, TIA/stroke, hypertension, peripheral vascular disease, atrial fibrillation, VTE, pulmonary embolism) / No If congestive cardiac failure, what is the NYHA: I / II / III / IV	– Admission clerking – Anaesthetic notes – Outpatient letters
8. History of respiratory disease	None / Dyspnoea on exertion or CXR (mild COPD) / Dyspnoea limiting exertion to <1 flight or CXR moderate COPD / Dyspnoea at rest/rate >30 at rest or CXR (fibrosis or consolidation)	
9. History of COPD	Yes / No	
10. History of chronic kidney disease	Yes (I / II / IIIA / IIIB / IV / V) / No	
11. History of liver cirrhosis	Yes / No	
12. History of diabetes mellitus	Yes - Type I / Yes - Type II (diet controlled, tablet controlled, insulin controlled) / No	
13. Active cancer and/or cancer treatment	Yes / No	
14. Inflammatory bowel disease	Yes / No	
15. Previous history of VTE	Yes / No	
16. Management of iron-deficiency anaemia	None / Preoperative iron supplementation / Tranexamic acid / RBC transfusion (If yes: 1, 2, 3, 4, ≥5 units)	
17. Preoperative treatment	Yes (Aspirin, ACEi/ARB, β-blocker, α ₂ agonist, rate controlling CCB, DHP CCB) / No If yes, was medication stopped preoperatively? (No / Yes, stopped preop only / Yes, stopped preop & postop)	– Clinical letters / notes PACS software
18. Preoperative therapeutic anticoagulation	Yes (Low Molecular Weight Heparin (LMWH), Warfarin, Direct acting oral anticoagulants (DOACs)) / No	– Clinical letters / notes PACS software

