2. Critical care bed days (if yes)	Number (days from first post-operative day to day of discharge from critical care. If the patient has not been discharged prior to the end of 30-day follow-up, enter '31').	
3. Postoperative haemoglobin	Not applicable / Available (day 0-1, day 1-3, day 4-6, last prior to discharge) If available, please state value in grams/litre	
4. Postoperative interventions for anaemia	None / iron supplementation / Tranexamic acid / RBC transfusion (If yes: 1, 2, 3, 4, ≥5 units)	
5. Cardiovascular complications within 30 days	None / Myocardial infarction / Myocardial injury / Non-fatal cardiac arrest / Coronary revascularisation / Pulmonary embolism (symptomatic non-fatal / asymptomatic) / Deep venous thrombosis (proximal / distal; if either symptomatic / asymptomatic) / New onset Atrial fibrillation / Stroke (select all that apply) *see Appendix D for definitions Please indicate the POD of the event(s) selected.	• Clinical notes • PACS software
6. Bleeding complications within 30 days	None / Major bleeding / Clinically relevant non-major bleeding *see Appendix D for definitions	
7. Post-operative length of stay	Number (days between from the first post-operative day to day of discharge. If the patient has not been discharged prior to the end of 30-day follow-up, enter '31').	
8. Highest 30-day complication grade	None / Clavien-Dindo Grade I-V (see Appendix D for the full 7-point Clavien-Dindo scale). If grade V, was death cardiac, PE or non-cardiac? (see Appendix D for definitions)	
9. 30-day Reoperation	Yes / No	
10. 30-day Readmission	Yes - planned / Yes- unplanned / No (this applies if patient had died during initial admission) If yes: what is the grade of complication (none, grade I, grade II, grade III, grade IV, grade V)	
11. 30-day postoperative COVID status	None / Preoperative / Postoperative If preoperative: are you still symptomatic (yes/no) and were you vaccinated (no / partial / full)	
12. Haemoglobin on readmission	Not available / Available If available, please state value in grams/litre	
13. Interventions for anaemia at readmission	None / iron supplementation (Oral / Intravenous), blood transfusion (If yes: 1, 2, 3, 4, ≥5 units)	
14. Postoperative outpatient VTE prophylaxis duration	Number (days of pharmacological VTE prophylaxis the patient was discharged home with)	

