15. Postoperative outpatient VTE prophylaxis	None / Low molecular weight heparin / Direct oral anticoagulants / Warfarin *If DOAC was selected, was this dabigatran, rivaroxaban, apixaban, edoxaban or betrixiban?	
--	--	--

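### The post-discharge thromboprophylaxis fields record the drug but not its intent, so patients sent home on therapeutic anticoagulation may be entered as extended prophylaxis or as none

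*Protocol*

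**What the plan says.** All places are in the protocol.

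- **Pre-operative item 18 (Appendix B)** is headed "Preoperative therapeutic anticoagulation" and is answered "Yes (Low Molecular Weight Heparin (LMWH), Warfarin, Direct acting oral anticoagulants (DOACs)) / No".
- **Post-operative item 14** asks for the "days of pharmacological VTE prophylaxis the patient was discharged home with".
- **Post-operative item 15** asks which agent: "None / Low molecular weight heparin / Direct oral anticoagulants / Warfarin". If a DOAC is chosen, its name is requested. The Appendix A box offers the same choices.
- **Pre-operative item 17** asks whether medication was stopped around surgery, but only for aspirin, ACE inhibitors/ARBs, beta-blockers, alpha-2 agonists and calcium-channel blockers. Anticoagulants are not covered.
- **Post-operative item 5** records new atrial fibrillation, DVT and PE, with the post-operative day of each event.
- **Section 6 (Covariates)** lists among the data for risk adjustment "smoking status, anticoagulant or antiplatelet use, preoperative blood test values".

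Items 14 and 15 serve the secondary aim "To characterise the efficacy and safety profile of extended pharmacological thromboprophylaxis in patients at high risk for VTE", the secondary outcome on length of prophylaxis (section 7), and post-operative audit standard 3, whose source guidance refers to 28 days after major abdominal cancer surgery. Patients on anticoagulants are not excluded (section 5).

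**The concern.** The form distinguishes therapeutic anticoagulation before surgery and drops the distinction at discharge, where the exposure is measured. Someone sent home on a treatment course of LMWH, a DOAC or warfarin has no fitting answer. Naming the drug places a treated patient among those given extended prophylaxis. Entering None places an anticoagulated patient in the comparison group and makes them appear to fail the 28-day standard.

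Two features add to the ambiguity. Long-term therapy has no natural number of days, and item 14 has no convention for it, whereas the critical-care and length-of-stay items tell collectors to enter 31 when the stay outlasts follow-up. Also, the rule that removes collection periods with more than 5% missing data pushes collectors to enter something.

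At stake is exposure classification in one secondary aim, one secondary outcome and one of the nine audit standards (five pre-, one intra- and three post-operative) that make up the primary outcome. Treatment newly started for an in-hospital DVT or PE is the most awkward case for efficacy: if it is entered as prophylaxis, the event that prompted the drug is counted against the drug.

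**Working it through.** **Stated figure.** 300 centres × 10 patients per week × 2 weeks = 6000, which reproduces section 9. The protocol gives no anticoagulation prevalence, uptake of extended prophylaxis or bleeding rate, so everything below is illustrative.

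**What the collected fields can separate**

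| Patient at discharge | Seen in item 18? | Seen in item 5? | Intent at discharge known? |
|---|---|---|---|
| Long-term anticoagulant resumed | Yes | Not needed | No: item 18 shows prior use, not resumption |
| Prior anticoagulant user sent home on prophylactic LMWH | Yes | Not needed | No: looks the same as resumed LMWH treatment |
| New treatment for post-operative DVT or PE | No | Yes, with day | Partly: event known, prescription intent not |
| New treatment for post-operative atrial fibrillation | No | Yes, with day | No: not every such patient is anticoagulated |

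**Assumed inputs (none is in the protocol).** Let *a* be the share on therapeutic anticoagulation, all of them prior users who resumed it: 2–10%. Let *q* be the share of the others given extended prophylaxis: 10–50%. Let *k* be the bleeding risk of the therapeutic group relative to the others: 2–3. Prophylaxis is assumed to have no true effect on bleeding, so the correct risk ratio is 1.00.

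**Formulas.** The base bleeding risk cancels.

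- All entered as prophylaxis: recorded uptake = a + (1−a)q; RR = [(1−a)q + ka] / [(1−a)q + a].
- All entered as None: recorded uptake = (1−a)q; RR = [(1−a)(1−q) + a] / [(1−a)(1−q) + ka].

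**One case in full: a = 5%, q = 30%, k = 2.**

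- Entered as prophylaxis: uptake 0.05 + 0.285 = 33.5%; RR = (0.285 + 0.10)/0.335 = 1.15. Therapeutic patients form 0.05/0.335 = 14.9% of the recorded prophylaxis group.
- Entered as None: uptake 28.5%; RR = 0.715/0.765 = 0.93.

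**Selected results**

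| a | q | k | RR, all entered as prophylaxis | RR, all entered as None |
|---|---|---|---|---|
| 2% | 50% | 2 | 1.04 | 0.96 |
| 2% | 10% | 2 | 1.17 | 0.98 |
| 5% | 30% | 2 | 1.15 | 0.93 |
| 10% | 10% | 3 | 2.05 | 0.82 |
| 10% | 50% | 3 | 1.36 | 0.73 |

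Over the whole grid the ranges are 1.04–2.05 and 0.73–0.98. A true uptake of 30% is recorded as 31.4–37.0% under the first coding and as 27.0–29.4% under the second.

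**Mixed coding.** If a fraction *c* of the therapeutic patients is entered as prophylaxis, they form the same share of both recorded groups when c/q = (1−c)/(1−q), that is, when c = q. The crude RR is then 1.00. It exceeds 1 if c > q and falls below 1 if c < q. Since c is set by the collectors' reading of the form, the direction cannot be known in advance.

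**Excluding item 18 = Yes.** Within this calculation the RR returns to 1.00, but only because every therapeutic patient was assumed to be a prior user. Newly started treatment stays in.

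**The case against.** The strongest reply is that item 18 records prior therapeutic anticoagulation by drug class for every patient. Those on long-term therapy can therefore be found, excluded, stratified or adjusted for, however item 15 was completed. Section 6 already names anticoagulant use as a confounder. New DVT, PE and atrial fibrillation carry a post-operative day that can be set against length of stay. Choosing the analysis set is ordinary SAP content, and the SAP is not shown. The dictionary does use different words for treatment and prophylaxis, and the compulsory e-learning has a module on pharmacological VTE prophylaxis whose content is not shown and might contain a coding rule.

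Much of this stands. A reader might infer that no field can separate the two groups, or that these patients are bound to be counted as prophylaxis or as none. The protocol supports neither: most long-term users are identifiable, and no analysis rule is stated. A reader might also infer that extended prophylaxis will look less safe than it is. That follows only if enough centres enter treated patients as prophylaxis; the opposite coding reverses it.

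What does not fall is the capture gap. Intent at discharge is not asked, so no analysis plan can recover it fully. Adjusting for a baseline covariate does not correct a misclassified exposure, and the dated events do not show what was prescribed.

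**Conclusion.** The point holds as a gap in data capture. Items 14 and 15 cannot distinguish prophylactic from therapeutic anticoagulation at discharge, and the protocol gives no rule for entering the second. Item 18 and item 5 allow partial separation only: they do not show whether earlier therapy was resumed or whether new treatment was prescribed.

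The size is unknown. It is tempting to read 2–10% of 6000, or 120 to 600 patients, as the number affected. That count rests on an assumed prevalence and takes all patients as its base, whereas the aim and standard 3 concern those at high VTE risk, whose number the protocol does not give. The risk ratios above are crude results, with all patients coded one way, under assumed inputs; they show that the distortion could be small or material, and in either direction.

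This is a cheap improvement rather than a flaw that undermines the study.

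**What to change.** Add one required sub-field to post-operative item 15 and to the matching Appendix A box, shown for any answer other than None: prophylactic; therapeutic, pre-existing indication; therapeutic, new indication. Restrict the extended-prophylaxis comparison and the standard-3 denominator to patients not discharged on therapeutic anticoagulation, and report the others as a separate group.

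If the form is closed:

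1. Exclude patients with item 18 = Yes from the comparison.
2. Handle patients with a DVT, PE or new atrial fibrillation dated before discharge separately, while still counting their VTE events as outcomes.
3. State the remaining misclassification as a limitation.

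The cost is one tick-box taken from the same discharge prescription, a sentence defining the analysis set, and a somewhat smaller group for that comparison. The change concerns recording and analysis only; it implies nothing about which anticoagulant, intensity or duration a patient should receive.

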Appendix C: Included Operative Procedures

Specialty	Procedures
Upper Gastrointestinal	
 • Oesophagogastrectomy (excision of oesophagus and stomach) • Oesophagectomy (excision of oesophagus). • Gastrectomy (excision of stomach). • Duodenectomy / Small bowel resection (excision of small bowel).
Hepatopancreatobiliary	
 • Cholecystectomy (total or partial excision of gallbladder). • Hepatectomy (segmental or partial excision of liver) • Excision of bile duct • Pancreatectomy (total or partial excision of pancreas, including Whipple's procedure). • Splenectomy (total or partial excision of spleen).
Lower gastrointestinal	
 • Appendicectomy (Total or partial excision of appendix). • Panproctocolectomy (total excision of colon and rectum). • Completion proctectomy • Pancolectomy (total excision of colon). • Subtotal colectomy • Ileocaecal resection • Right colectomy (excision of right colon; including extended). • Transverse colectomy (excision of transverse colon). • Left colectomy (excision of left colon; including extended). • Sigmoid colectomy (excision of sigmoid colon). • Excision of rectum (including abdominoperineal resection, anterior resection or Hartmann's procedure).
Stoma	
 • Formation, reversal or closure of ileostomy. • Formation, reversal or closure of colostomy (include reversal of Hartmann's). • Formation of urostomy (including ileal conduit, Kock pouch, Indiana pouch, Mitrofanoff procedure and ileal neobladder).
Vascular	
 • Open replacement or repair of aneurysmal segment of aorta. • Vascular bypass surgery including abdominal component (e.g. aortobifemoral or aortounifemoral bypass)
Endocrine	
 • Adrenalectomy (excision of adrenal gland).
Transplant	
 • Transplantation of liver • Transplantation of pancreas (or islet cell transplantation) • Transplantation of kidney • Live donor nephrectomy (excision of kidney for transplant indication) • Transplantation of bowel
Gynaecology	
 • Trachelectomy or cervicectomy (excision of cervix uteri). • Hysterectomy (total or partial excision of uterus). • Salpingo-oophorectomy (total or partial excision of fallopian tube or ovary).

Urology	
• Nephrectomy (total or partial excision of kidney).• Ureterectomy (excision of ureter).• Cystectomy (total or partial excision of bladder).• Prostatectomy (total or partial excision of prostate).
Hernia	
• Anterior abdominal wall incisional hernia repair.• Parastomal hernia repair.
Other	
• Multivisceral resection (resection of several viscera in combination, including pelvic exenteration)• Other (free text)

Appendix D: Definitions of Key Outcomes

A. Cardiovascular complications:

There are several factors which can increase the risk of postoperative cardiovascular complications in the perioperative content, particularly in patients with pre-existing cardiac disease.

There are heterogenous definitions with the medical literature regarding which conditions should be considered postoperative cardiovascular complications (and how these should be defined). This makes it difficult to interpret new studies in the context of the existing literature, and so means it often is not possible to pool the data within systematic reviews.

A recent systematic review and international consensus process¹³ recommended redefining postoperative cardiovascular outcomes that can be used in future trials to measure the effectiveness of perioperative interventions. The following outcomes are included within the new definition of perioperative cardiovascular adverse events:

1. **Atrial fibrillation:** New onset of irregularly irregular heart rate in the absence of P wave lasting at least 30 s or for the duration of the ECG recording (if <30 s)
2. **Myocardial infarction:** Acute myocardial injury with clinical evidence of acute myocardial ischaemia and with detection of an increase or decrease in cardiac troponin (cTn) values with at least one value above the 99th percentile upper reference limit (URL) and at least one of the following:
 - a. Symptoms of myocardial ischaemia
 - b. New ischaemic ECG changes
 - c. Development of pathological Q waves
 - d. Imaging evidence of new loss of viable myocardium or new regional wall motion abnormality in a pattern consistent with an ischaemic aetiology
 - e. Identification of a coronary thrombus by angiography or autopsy - Post-mortem demonstration of acute atherothrombosis in the artery supplying the infarcted myocardium.

Cardiac death in patients with symptoms suggestive of myocardial ischaemia and presumed new ischaemic ECG changes before cTn values become available.

- 3. Myocardial injury:** Detection of an elevated cTn value above the 99th percentile URL is defined as myocardial injury. The injury is considered acute if there is an increase or decrease in cTn values
- a. Note: it is not clinically possible to distinguish which increases of cTn levels are attributable to which mechanisms
 - b. A diagnosis of myocardial infarction requires an increase of cTn values and evidence of myocardial ischaemia that may be evident from the peri- and postoperative period (e.g. ST segment changes on telemetry/ECG, repeated episodes of hypoxia, hypotension, tachycardia, or imaging evidence of myocardial injury)
 - c. In the absence of evidence for acute myocardial ischaemia, the diagnosis is acute myocardial injury
- 4. Coronary revascularisation:** Cardiac revascularisation procedure was defined as percutaneous coronary intervention or coronary artery bypass graft surgery within 30 days of the index surgery.
- 5. Cardiac death:** Death with a vascular cause and included those deaths after a myocardial infarction, cardiac arrest, and cardiac revascularisation procedure.
- a. Excludes:
 - i. Death after pulmonary embolism
 - ii. Death after haemorrhage
 - iii. Death after multi-organ failure
 - iv. Cause of deaths unknown
- 6. Non-fatal cardiac arrest:** Successful resuscitation from either documented or presumed ventricular fibrillation, sustained ventricular tachycardia, asystole, or pulseless electrical activity requiring cardiopulmonary resuscitation, pharmacological therapy, or cardiac defibrillation
- 7. Major adverse cardiac event:** A composite outcome that should include:
- a. Cardiac death (as defined previously)
 - b. Myocardial infarction (as defined previously)

- c. Non-fatal cardiac arrest (as defined previously)
- d. Coronary revascularisation (as defined previously) within 30 days of index surgery
- e. *Excludes* - Pulmonary embolism, haemorrhage, deep venous thrombosis, all-cause mortality

8. Pulmonary embolism may present as sudden death, breathlessness, faintness, collapse or chest pain. Diagnosis of pulmonary embolism requires any one of following:

- a. A high probability ventilation/perfusion lung scan
- b. An intraluminal filling defect of segmental or larger artery on a helical CT scan
- c. An intraluminal filling defect on pulmonary angiography
- d. A positive diagnostic test for deep venous thrombosis (e.g. positive compression ultrasound) and one of the following:
 - i. Non-diagnostic (i.e. low or intermediate probability) ventilation/perfusion lung scan
 - ii. Non-diagnostic (i.e. sub-segmental defects or technically inadequate study) helical CT scan

9. Deep vein thrombosis (DVT) is defined as the formation of a thrombus (blood clot) in a deep vein.

- a. Diagnosis of DVT requires any one of the following:
 - i. A persistent intraluminal filling defect on contrast venography
 - ii. Non-compressibility of one or more venous segments on B-mode compressionultrasonography
 - iii. A clearly defined intraluminal filling defect on contrast enhanced CT
- b. DVT can be divided in proximal and distal³¹:
 - i. Proximal DVT is defined as DVT in the popliteal vein and/or higher (femoral vein, common femoral vein, iliac vein, vena cava).
 - ii. Distal DVT (calf DVT) is defined as DVT in at least 1 of the 3 major paired veins (posterior tibial, anterior tibial, peroneal) in the calf, below the popliteal vein.
- c. DVT can be also divided in symptomatic and asymptomatic³¹:
 - i. Symptomatic DVT is defined as leg pain and swelling resulting from thrombotic occlusion of a major leg vein. It requires specific investigation and treatment.

- ii. Asymptomatic DVT is defined as DVT detected by screening with ultrasound or ascending venography, and with no associated symptoms (leg pain and swelling).

10. Stroke: Embolic, thrombotic, or haemorrhagic event lasting at least 30 min with or without persistent residual motor, sensory, or cognitive dysfunction; if the neurological symptoms continue for >24hrs, a person is diagnosed with stroke, and if lasting ,24 h the event is defined as a transient ischaemic attack³²

B. Bleeding outcomes

Bleeding is an important safety outcome in studies exploring the use of anticoagulation pharmacological therapies. To ensure consistency across research studies, a validated and clinically relevant classification should be used. In the CASCADE study, we have adopted the definitions of bleeding outcomes recommended by the European Medicines Agency.

Major bleeding³³ is defined as a bleeding event that meets at least one of the following criteria:

- fatal bleeding
- critical bleeding (intracranial, intraocular, intraspinal, pericardial, retroperitoneal, in a non-operated joint, or intramuscular with compartment syndrome)
- clinically overt bleeding (at surgical or extrasurgical site) associated with a decrease in the haemoglobin level of more than 2 g/dL (20 g/l; 1.24 mmol/L) compared with the pre-operative level
- clinically overt bleeding (at surgical or extrasurgical site) leading to transfusion of two or more units of whole blood or packed cells
- bleeding located at the surgical site and leading to re-operation or to any unusual medical intervention or procedure for relief (e.g. draining or puncture of an haematoma at the surgical site, transfer to an ICU or emergency room).

Clinically relevant non-major bleeding^{33,34} is defined as any clinically overt bleeding that:

- does not meet the criteria for major bleeding BUT
- requires medical attention (e.g.: hospitalisation, medical treatment for bleeding) AND/OR a change in antithrombotic therapy (including discontinuation or down-titration) AND/OR any other bleeding type considered to have clinical consequences for a patient.

Examples of clinically relevant non-major bleeding are:

- multiple-source bleeding;
- spontaneous haematoma >25 cm², or > 100 cm² if there was a traumatic cause;
- intramuscular haematoma documented by ultrasonography without compartment syndrome;
- excessive wound haematoma not requiring draining or puncture;
- macroscopic haematuria (spontaneous or lasting >24 h if associated with an intervention);
- epistaxis or gingival bleeding that requires tamponade or other medical intervention;

- haemoptysis, haematemesis or spontaneous rectal bleeding requiring endoscopy or other medical intervention.

C. Clavien-Dindo Classification System:

Adverse post-operative events may be classified in different ways:

- **Failure of treatment** - This occurs when the original surgery fails to achieve its intended benefits; for example, persistent pain following laparoscopic cholecystectomy or tumour recurrence following cancer surgery.
- **Sequelae**: The recognised consequences of a given procedure; for example, gut malabsorption following a large small bowel resection or immune deficiency following splenectomy.
- **Complication**: Any deviation from the normal post-operative course that has an adverse effect on the patient and is not either a treatment failure or sequel.

In the Clavien-Dindo classification ³⁵, the factor determining the severity of a complication is the treatment required. Consequently, a given complication may be graded differently depending on how it has been managed. For example, an anastomotic leak may be managed just with antibiotics if it is contained (grade II) or it may require re-operation under anaesthetic (grade IIIb).

Some other considerations:

- Intra-operative complications are not considered unless they have an adverse effect on the patient post-operatively. The only exception to this is intra-operative death; this is classified as grade V.
- All post-operative adverse events are included, even when there is no direct relationship to the surgery.
- All adverse events within the follow-up period (30 days) are included, even after following discharge.
- Diagnostic procedures are not included. For example, a diagnostic oesophagoduodenoscopy (OGD) to look for a source of bleeding without any intervention would not be considered a complication, but a therapeutic OGD with clipping of a bleeding vessel would be considered a grade IIIa complication. Since negative exploratory laparotomies are considered to be diagnostic procedures, they should not be recorded as complications.

Grade	Definition (examples listed in italics)
I	
Any deviation from the normal postoperative course without the need for pharmacological (other than “allowed therapeutic regimens”), surgical, endoscopic or radiological intervention.
 
Allowed therapeutic regimens are: selected drugs (antiemetics, antipyretics, analgesics, diuretics and electrolyte replacement), physiotherapy and wound infections opened at the bedside but not treated with antibiotics.
 
Examples: Ileus (deviation from the norm); hypokalaemia treated with K; nausea treated with cyclizine; acute kidney injury treated with intravenous fluids.

II	
Requiring pharmacological treatment with drugs beyond those allowed for grade I complications. Blood transfusions and total parenteral nutrition are also included.
 
Examples: Surgical site infection treated with antibiotics; myocardial infarction treated medically; deep venous thrombosis treated with enoxaparin; pneumonia or urinary tract infection treated with antibiotics; blood transfusion for anaemia.

IIIa	
Requiring surgical, endoscopic or radiological intervention, not under general Anaesthetic (GA).
 
Examples: Therapeutic endoscopic therapy (do not include diagnostic procedures); interventional radiology procedures.

IIIb	
Requiring surgical, endoscopic or radiological intervention, under GA.
 
Examples: Return to theatre for any reason.

IVa	
Life-threatening complications requiring critical care management with single organ dysfunction, or neurological complications including brain haemorrhage and ischemic stroke (excluding TIA).
 
Examples: Single organ dysfunction requiring critical care management, e.g. pneumonia with ventilator support, renal failure with filtration; SAH; stroke

IVb	
Life-threatening complications requiring critical care management with multi-organ dysfunction.

